**2.3.2. Prevention of breast cancer in genetically engineered mice.** The FVB/N-TgN (MMTVneu)-202Mul mouse (TgMMTV-neu) develop spontaneous mammary cancer. The tumors arising in this and other genetically engineered mice, share significant similarities with human breast cancer at both the molecular and protein level. Indeed, spontaneously arising mammary cancers in these animals express HER2, IGF-1R and IGFBP-2 and investigations have shown that growth of syngeneic implanted tumors can be significantly delayed by vaccinating mice with peptides, derived from each of these proteins, designed to elicit antigen specific CD4+ T-cells. TgMMTV-neu is a stringent model for assessing prophylactic vaccination. Mechanisms of both central and peripheral tolerance significantly limit the ability to successfully immunize these mice. The mice are tolerant to their tumors and T-cells derived from tumor draining lymph nodes do not secrete IFN-g when challenged with antigen. The lack of Type I IFN-g secreting tumor antigen specific T-cells has also been well described in breast cancer patients. IFN-g is needed for tumor recognition through activating antigen presenting cells (APC) to engage T-cells. If T-cells are induced by vaccination in this model, the response is short lived unless vaccine formulations include molecules to significantly enhance co-stimulation, thus, potentially increasing the risk for autoimmune toxicity. Several prophylactic vaccine approaches have been evaluated in the TgMMTV-neu. The extent of protection in these studies was variable and vaccine efficacy decreased significantly with age at immunization.

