We immunized 18 week old mice (15 mice/group) to model the clinical translation of such an approach to mature adult women, with high risk of developing breast cancer, who would likely be the target population for prophylactic vaccination. The mouse homologues of all three proteins, IGFBP-2, IGF-1R and HER2, demonstrated expression in hyperplastic mammary lesions in TgMMTV-neu mice. Fifty percent of multi-antigen immunized mice did not develop breast cancer as compared with 0% of controls ( $p<0.0001$ ) at approximately 1 year. The median disease-free-survival (DFS) of vaccinated animals was significantly longer than those mice receiving adjuvant alone, 46 vs. 30 weeks (HR 3.959, CI 2.018 to 7.768). At experiment termination, overall survival (OS) was also significant between the two groups ( $p<0.0002$ ). The median OS of the vaccinated animals had not been reached while the median OS of the control group was 40 weeks (HR 4.335, CI 1.886-9.962). The use of a multi-antigen vaccine was significantly more effective in improving DFS than immunizing with the individual antigens alone. In a repeat experiment, mice immunized with a HER2-specific vaccine demonstrated a median DFS of 38 weeks as compared to 28 weeks in adjuvant controls ( $p=0.251$  between groups). The DFS was 38 weeks for IGF-1R immunized mice ( $p=0.367$ ) and 37 weeks for IGFBP-2 vaccinated animals ( $p=0.251$ ) compared to adjuvant controls. In the multi-antigen vaccinated cohort, 80% of the mice remained tumor free and the median DFS for the multi-antigen vaccinated mice was not reached at the time of experiment termination ( $p=0.0013$  compared to control). In addition, while the DFS of the single antigen vaccinated animals was not different from each other ( $p=0.965$ ) the multi-antigen vaccine significantly prolonged DFS compared to any of the single antigen approaches ( $p=0.018$ ). To evaluate whether antigen coverage provided by the vaccine would effectively inhibit the growth of additional mammary cancer phenotypes, TgC3(I)-Tag mice, a model of basal breast cancer, were immunized and then challenged with syngeneic tumor. Tumor growth was significantly inhibited ( $p<0.00001$ ) in the multi-antigen vaccinated mice as compared to the adjuvant immunized controls. Indeed, tumor inhibition occurred despite the fact spontaneous tumors in these mice show expression of only IGF-1R and IGFBP-2 but not HER2.

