## 4. PATIENT SELECTION

### 4.1 Inclusion Criteria

- 4.1.1. Patients with non-metastatic, node positive, HER2 negative breast cancer, confirmed by pathology report, who are in remission and defined as having no evidence of disease (NED). HER2 negative is defined as
  - a. 0-1+ HER2 expression by immunohistochemistry (IHC) OR
  - b. Fluorescence in situ hybridization (FISH) negative OR
  - c. HER2 2+ and FISH negative
- 4.1.2. Patients must be at least 28 days post cytotoxic chemotherapy, radiotherapy, monoclonal antibody and/or other biologic therapy, prior to enrollment. Patients on bisphosphonates, denosumab, and/or

endocrine therapy administered during the study are eligible and may continue throughout duration of study.

- 4.1.3. Patients must be at least 28 days post systemic steroids prior to enrollment.
- 4.1.4. Patients must be at least 18 years of age.
- 4.1.5. Patients must have Eastern Cooperative Oncology Group (ECOG) Performance Status Score of  $\leq 2$ .
- 4.1.6. Adequate laboratory values within 90 days of enrollment defined as follows:
  - a. White blood cell (WBC)  $\geq 3000/\text{mm}^3$
  - b. Hemoglobin (Hgb)  $\geq 10 \text{ g/dL}$
  - c. Lymphocyte count  $\geq 800/\text{mm}^3$
  - d. Platelet count  $\geq 75,000/\text{mm}^3$
  - e. Serum creatinine  $\leq 2.0 \text{ mg/dL}$  or creatinine clearance  $> 60 \text{ ml/min}$
  - f. Total bilirubin  $\leq 1.5 \text{ mg/dL}$
  - g. Aspartate aminotransferase (AST)/Serum glutamic oxaloacetic transaminase (SGOT)  $\leq 2$  times upper limit of normal (ULN)
  - h. HbA1c  $< 5.7\%$
- 4.1.7. Patients must have recovered from major infections and/or surgical procedures, and in the opinion of the investigator, not have any significant active concurrent medical illnesses precluding protocol treatment.
- 4.1.8. The effects of WOKVAC on the developing human fetus are unknown. For this reason, patients who are having sex that can lead to pregnancy must agree to use adequate contraception (hormonal, barrier method of birth control, or abstinence) for the duration of study participation. Should a woman become pregnant while participating in the study, she should inform her study doctor immediately and will not receive any more study treatment.
- 4.1.9. LVEF results must be  $\geq$  lower limit of normal (LLN) for institution performing based on results from the MUGA or ECHO done at baseline.

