## **13. STATISTICAL CONSIDERATIONS**

### **13.1 Study Design/Description**

This is a phase I non-randomized, dose - escalation study of safety and immunogenicity of a triple antigen vaccine. The study population consists of relatively healthy and stable patients with history of breast cancer.

Patients will be assigned sequentially to one of three arms defined by vaccine dose. Patients will be accrued to Arm 1 first, then Arm 2, and Arm 3.

- Arm 1: WOKVAC (150 mcg) with rhuGM-CSF (100 mcg); administered i.d. every month for 3 total doses.
- Arm 2: WOKVAC (300 mcg) with rhuGM-CSF (100 mcg); administered i.d. every month for 3 total doses.
- Arm 3: WOKVAC (600 mcg) with rhuGM-CSF (100 mcg); administered i.d. every month for 3 total doses.

If there is sufficient evidence (please see Section 8.5.1. Criteria for Premature Study Termination) to suggest the Arm 1 dose is safe; the Arm 2 cohort of up to 12 patients will be enrolled. If the Arm 2 dose is also regarded as sufficiently safe, the Arm 3 cohort of up to 12 patients will be enrolled. If the Arm 3 dose appears safe, the immunologic efficacy among three dose groups will be examined to determine the recommended phase 2 dose for further cancer prevention studies. For the phase 2 study, safety and immunologic efficacy decisions will be made on the evaluation of data from the three possible doses.

After the Arm 3 dose, key study personnel in concert with the NCI/DCP staff will review the immunologic efficacy data along with safety with other laboratory findings to make a decision on an appropriate phase 2 dose.

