### **13.2 Randomization/Stratification**

N/A.

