Analyses of the above secondary endpoints will be descriptive in nature by necessity. Despite lack of randomization, we will compare the immunologic efficacy between the 3 dose levels data using linear dose-response relationship with a regression analysis. Normalizing transformation will be used as well if necessary. The linear regression model will have a 0.80 power to detect an anticipated effect size (defined as  $R_2/(1-R_2)$ ) of 0.281 according to the level 0.05 F-test, given the sample size of 30.

Once the dose escalation is completed, key study personnel in concert with the NCI/DCP staff will review the toxicity, immunogenicity, antibody immune response, memory T cell response, Treg, and MDSC, and make a recommendation for a phase 2 dose. Statistical tests will only be advisory due to lack of randomization and limited sensitivity of such tests given the small sample size for each dose group. We may seek other experts in this deliberation.

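### The dose-response regression of immune response has no age term, although age is a plausible confounder across the sequentially filled, non-randomised dose arms

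*Combined protocol and SAP*

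**What the plan says.** Section 2.3.2 describes earlier prophylactic vaccines tested in the TgMMTV-neu mouse, the model the sponsor also used: "The extent of protection in these studies was variable and vaccine efficacy decreased significantly with age at immunization". The sponsor's own experiment used a single age: "We immunized 18 week old mice (15 mice/group) to model the clinical translation of such an approach to mature adult women".

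The only age criterion in section 4.1 is "Patients must be at least 18 years of age"; there is no upper limit. Section 13.1 allocates by order of entry: "Patients will be accrued to Arm 1 first, then Arm 2, and Arm 3". The entry under "13.2 Randomization/Stratification" is N/A.

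On the dose comparison, section 13.5 says: "Despite lack of randomization, we will compare the immunologic efficacy between the 3 dose levels data using linear dose-response relationship with a regression analysis". It names no covariate. Its power statement reads: "The linear regression model will have a 0.80 power to detect an anticipated effect size", defined there as R²/(1-R²), "of 0.281 according to the level 0.05 F-test, given the sample size of 30". The same section calls the secondary analyses descriptive and the tests advisory, and it gives the lack of randomization as a reason. Section 13.4 provides for a descriptive summary of baseline characteristics, without saying that it will be by arm.

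**The concern.** Arms filled in sequence can differ in age mix, because the patients who come forward may change over time or simply by chance. If age affects the immune response, a regression on dose alone attributes part of the age difference to dose. If later arms are older and response falls with age, the slope is pulled down and favours a lower dose. If later arms are younger, it is pulled up.

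The dose comparison matters to the sponsor. Section 13.9 expects immunogenicity to be the endpoint that moves the programme forward, and allows that the most immunogenic dose may not be the highest. Sections 8.2 and 13.5 feed immunogenicity into the phase 2 dose. The plan concedes that the arms are not randomised, but it names no confounder and plans no adjustment. Age is one candidate that its own background mentions and that is known for every patient.

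**Working it through.** **1. The plan's own figure.** Inputs from section 13.5: f² = 0.281, N = 30, alpha = 0.05. For one slope, u = 1, v = 30 - 2 = 28, and the noncentrality is N·f² = 30 × 0.281 = 8.43. The noncentral F distribution gives power 0.8003, so the stated 0.80 reproduces. The f² needed for 0.80 power is 0.2808 with dose alone (v = 28) and 0.2816 with one further term (v = 27). The stated 0.281 therefore fits a model with dose as the only predictor. Testing two predictors jointly would give 0.690.

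**2. Assumptions for the rest.** The documents give neither an age distribution nor an age effect in patients. I assume 10 evaluable patients per arm (section 13.9), age in SD units with arm means 0, Δ/2 and Δ, a within-arm age-response correlation ρ, and no dose effect.

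**3. Chance imbalance.** The difference in mean age between Arms 1 and 3 has SD √(2/10) = 0.447 SD. The chance that it exceeds 0.5 SD is 2[1 - Φ(0.5/0.447)] = 2[1 - Φ(1.118)], about 26%. Such imbalance can distort the one trial that is run, but over repeated trials it is already part of the test's error (Δ = 0 in step 5).

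**4. Bias from systematic drift.** The doses are 150, 300 and 600 mcg. Their mean is 350, the deviations are -200, -50 and +250, and the mean square is (40,000 + 2,500 + 62,500)/3 = 35,000. For Δ = 1 the age deviations are -0.5, 0 and +0.5, and the mean cross-product is (100 + 0 + 125)/3 = 75. The fitted age difference between 600 and 150 mcg is (75/35,000) × 450 = 0.964 SD. Multiplied by ρ, the bias in the fitted contrast is -0.29 SD (ρ = -0.3) or -0.48 SD (ρ = -0.5). For Δ = 0.5 it is half of this: -0.14 or -0.24 SD.

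**5. Rejection rate of the nominal 5% slope test** (simulation, 40,000 trials per cell):

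| Drift Δ, Arm 1 to Arm 3 | ρ | Dose alone | Dose + age |
|---|---|---|---|
| 0 | -0.3 | 5.1% | 4.9% |
| 0 | -0.5 | 5.2% | 4.9% |
| 0.5 SD | -0.3 | 6.3% | 5.1% |
| 0.5 SD | -0.5 | 8.0% | 5.1% |
| 1 SD | -0.3 | 10.0% | 5.0% |
| 1 SD | -0.5 | 18.5% | 4.8% |

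**6. Power with the age term.** The noncentrality is 8.43(1 - r²)/(1 - ρ²) with v = 27, where r is the dose-age correlation.
- No drift (r = 0): 8.43, 8.43/0.91 = 9.26 and 8.43/0.75 = 11.24 for |ρ| = 0, 0.3 and 0.5. Power is 0.799, 0.835 and 0.898.
- 1 SD drift: the age variance is 1 + (0.25 + 0 + 0.25)/3 = 1.167, so r = 75/√(35,000 × 1.167) = 0.371 and 1 - r² = 0.862. The noncentrality is 7.27, 7.99 and 9.69. Power is 0.74, 0.78 and 0.85.

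The cost is thus negligible when age is balanced. It is visible when age drifts with dose, which is also when adjustment is most useful.

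**The case against.** The strongest case against has four parts.

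- **The animal finding does not transfer directly.** It concerns earlier vaccines, and its outcome is tumour protection in mice that develop tumours spontaneously. This trial measures ELISPOT, antibody and flow-cytometry responses in patients without evidence of disease. The sponsor's own experiment used one age, so it says nothing about an age effect. This stands. A reader might infer that the protocol itself shows age lowers the response to WOKVAC; it does not.
- **The plan already discounts the tests.** Section 13.5 treats them as advisory, and the phase 2 dose is a joint judgement on toxicity, immunogenicity, antibody, memory T cells, Treg and MDSC. This stands and limits the weight of the point. A reader might take the dose slope to be the only inferential input on immunogenicity, but section 13.5 also plans mixed-effects models for ELISPOT, memory T cells, Treg and MDSC. Disclosing the weakness is still not a remedy for it, and advisory evidence informs the choice.
- **No drift is shown.** Eligibility is the same in every arm, and without systematic drift the unadjusted test keeps its level. This stands. The inflated rates are conditional.
- **Age is one candidate among several.** Section 2.3.3 names pre-existing MDSC and Treg levels as influences on vaccination; site and time since treatment are also unadjusted. This stands as a limit on what an age term can do. It is not a reason to omit it.

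**Conclusion.** The point holds as a modest one. The planned regression uses dose alone in a sequential, non-randomised comparison with no upper age limit, and the protocol's background makes age a plausible confounder of the advisory dose-response evidence. It does not affect the primary safety endpoint or the escalation rules.

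The size is conditional on an assumed drift and an assumed age-response correlation of -0.3 to -0.5. The false-positive rate is about 5% with no drift, 6% to 8% at 0.5 SD and 10% to 18% at 1 SD, against about 5% with age in the model.

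Three stronger readings are tempting and unsupported:
- That the test is inflated in this trial. That needs a systematic drift which the documents do not show.
- That adjustment costs only one degree of freedom. Under the 1 SD drift that produces the largest inflation, adjusted power is 0.74 to 0.85.
- That an age term would remove the bias. A linear term handles linear confounding by age and leaves the other differences between unrandomised arms.

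**What to change.** In section 13.5, prespecify as a sensitivity analysis the dose-response regression of immune response with age at first vaccination as a continuous covariate. Report the dose slope and its confidence interval with and without age, and in section 13.4 state that age will be tabulated by dose arm. Reporting both slopes shows the reader whether age matters and how much precision the adjustment gave up. Prespecifying it avoids a choice of covariate after the results are known.

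The cost is a sentence or two in the plan. It needs no new data, visits or patients. The primary dose-only regression and its power statement stay as they are, and the power loss set out above applies only to the adjusted analysis.

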### **3. SUMMARY OF STUDY PLAN**

This will be a Phase I, non-randomized, dose escalation study in patients with node positive non-metastatic HER2 negative breast cancer that are in remission and defined as no evidence of disease (NED). The study will accrue 30 evaluable patients with up to 12 patients in each dose arm.

Patients will be assigned sequentially to one of three arms defined by vaccine dose. Patients will be accrued to Arm 1 first, then Arm 2, then Arm 3. Each dose arm will have a staggered enrollment. There will be one week between the first patient's vaccination 1 visit and second patient's vaccination 1 visit to each dose arm to ensure no toxicities. Furthermore, three patients will initially be enrolled to a dose arm, receive the first vaccine, and be evaluated for toxicity prior to the second vaccine (1 month of monitoring) before the remaining patients will be enrolled in that dose arm.

If there is sufficient evidence (please refer to Section 8.5.1“Accrual and Criterion for Premature Study termination”.) to suggest the Arm 1 dose is safe (Section 13.1), then the Arm 2 cohort of up to 12 patients will be enrolled. If the Arm 2 dose is also sufficiently safe then enrollment into the Arm 3 dose may move forward. If the Arm 3 dose appears safe, the immunologic efficacy among three dose groups will be examined to determine the recommended phase 2 vaccine dose for further cancer prevention studies. Immunologic efficacy of the 3 WOKVAC doses, will be evaluated by an assessment of the generation of cellular and humoral response to IGFBP-2, HER2, and IGF-1R, development of persistent T cell memory; and modulation of Tregs and MDSC with vaccination as described in Section 13.5.

We will be evaluating the effect of the WOKVAC vaccine on the heart by measuring left ventricular ejection fraction (LVEF) with a MUGA or ECHO before vaccination, one month after the first vaccine, and one month after the vaccination series.

Clinical and autoimmune labs will be drawn prior to each vaccine and 1 month and 6 months following the last vaccine to evaluate for safety. Patients are monitored for the development of toxicities by assessing adverse events (AE's) with serum chemistries, liver function studies, and complete blood counts. Adverse events for all systems are graded on a scale of 1-5 using the Common Terminology Criteria for Adverse Events Version 4.0 (CTCAE v4.0). We will be using the Cancer Therapy Evaluation Program (CTEP), National Cancer Institute (NCI) Guidelines for reporting adverse events assigning attribution (unrelated, unlikely, possible, probable, definite) Blood samples to test the effect on the immune system will be drawn at baseline, and 1 month (28±7 days) and 6 months (168±14 days) following the last vaccine. The specific measurements being done to evaluate immune response are memory T cell response, modulation of Treg, and MDSC.

The duration of the study will be 5 years, which includes annual follow-up from enrollment, with the subject's primary oncologist or primary care physician. Long-term follow up data, beyond the 6 month follow-up visit, will be kept and managed by the IND Sponsor at the University of Washington.

## 4. PATIENT SELECTION

### 4.1 Inclusion Criteria

- 4.1.1. Patients with non-metastatic, node positive, HER2 negative breast cancer, confirmed by pathology report, who are in remission and defined as having no evidence of disease (NED). HER2 negative is defined as
  - a. 0-1+ HER2 expression by immunohistochemistry (IHC) OR
  - b. Fluorescence in situ hybridization (FISH) negative OR
  - c. HER2 2+ and FISH negative
- 4.1.2. Patients must be at least 28 days post cytotoxic chemotherapy, radiotherapy, monoclonal antibody and/or other biologic therapy, prior to enrollment. Patients on bisphosphonates, denosumab, and/or

endocrine therapy administered during the study are eligible and may continue throughout duration of study.

- 4.1.3. Patients must be at least 28 days post systemic steroids prior to enrollment.
- 4.1.4. Patients must be at least 18 years of age.
- 4.1.5. Patients must have Eastern Cooperative Oncology Group (ECOG) Performance Status Score of  $\leq 2$ .
- 4.1.6. Adequate laboratory values within 90 days of enrollment defined as follows:
  - a. White blood cell (WBC)  $\geq 3000/\text{mm}^3$
  - b. Hemoglobin (Hgb)  $\geq 10 \text{ g/dL}$
  - c. Lymphocyte count  $\geq 800/\text{mm}^3$
  - d. Platelet count  $\geq 75,000/\text{mm}^3$
  - e. Serum creatinine  $\leq 2.0 \text{ mg/dL}$  or creatinine clearance  $> 60 \text{ ml/min}$
  - f. Total bilirubin  $\leq 1.5 \text{ mg/dL}$
  - g. Aspartate aminotransferase (AST)/Serum glutamic oxaloacetic transaminase (SGOT)  $\leq 2$  times upper limit of normal (ULN)
  - h. HbA1c  $< 5.7\%$
- 4.1.7. Patients must have recovered from major infections and/or surgical procedures, and in the opinion of the investigator, not have any significant active concurrent medical illnesses precluding protocol treatment.
- 4.1.8. The effects of WOKVAC on the developing human fetus are unknown. For this reason, patients who are having sex that can lead to pregnancy must agree to use adequate contraception (hormonal, barrier method of birth control, or abstinence) for the duration of study participation. Should a woman become pregnant while participating in the study, she should inform her study doctor immediately and will not receive any more study treatment.
- 4.1.9. LVEF results must be  $\geq$  lower limit of normal (LLN) for institution performing based on results from the MUGA or ECHO done at baseline.
- 4.1.10. Willing to not undergo any elective surgical procedure with general anesthesia or conscious sedation through the 1 month post-vaccination visit.
- 4.1.11. Ability to understand and the willingness to sign a written informed consent document.

## 4.2 Exclusion Criteria

- 4.2.1. Patients with any of the following cardiac conditions:
  - a. Symptomatic restrictive cardiomyopathy
  - b. Dilated cardiomyopathy
  - c. Unstable angina within 4 months prior to enrollment
  - d. New York Heart Association functional class III-IV heart failure on active treatment
  - e. Symptomatic pericardial effusion
- 4.2.2. Patients may not be receiving any other investigational agents.

- 4.2.3. History of allergic reactions attributed to compounds of similar chemical or biologic composition to WOKVAC.
- 4.2.4. Patients with any contraindication or known hypersensitivity to receiving rhuGM-CSF or other yeast based products.
- 4.2.5. Pregnant women are excluded from this study because WOKVAC is a vaccine agent with unknown potential for teratogenic or abortifacient effects. Because there is an unknown but potential risk for adverse events in nursing infants secondary to treatment of the mother with WOKVAC, breastfeeding should be discontinued if the mother is treated with this vaccine.
- 4.2.6. History of diabetes.
- 4.2.7. Known history of human immunodeficiency virus (HIV) infection, hepatitis B, or hepatitis C.
- 4.2.8. History of autoimmunity that has not been controlled with treatment in the last 12 months.

